An x-ray of the wrist for the assessment of bone age will be obtained at Screening and at Week 52/Premature Discontinuation visit to determine changes in bone maturation. Sites should use the Greulich and Pyle method for reading the x-ray.²⁰ The x-ray report requires the signature of the radiologist who read the films or of the investigator. The bone age that is determined by the x-ray should be recorded on the eCRF. Assessment of bone age will not be required for subjects with the Premature Discontinuation visit at or before Week 26. An x-ray of the wrist for the assessment of bone age at Screening will

not be required if the subject had an x-ray within 90 days of Screening, provided all protocol required documentation is available at the site.

Anthropometric Evaluations

Height and weight obtained at Baseline, Week 26 and Week 52/Premature Discontinuation will be used by AbbVie Data Management and Statistical groups for determination of BMI and "z" score (observed height velocity [cm/yr] – mean height velocity for age and sex [cm/yr]/SD of the mean) for height.

At Baseline, height from 6 months prior to Screening and maximal weight attained within preceding 6 months will be recorded.

Tanner Stage

Tanner Stage will be assessed at Screening (or at Baseline as appropriate), Week 26 and Week 52/Premature Discontinuation Visit if premature discontinuation occurs after Week 26. Tanner Staging should be captured on the appropriate eCRF page.

Pediatric Ulcerative Colitis Activity Index (PUCAI)

A PUCAI score will also be calculated at all study visits beginning at Baseline.

An example of the PUCAI is located in [Appendix C](#).

The PUCAI score will be assessed using subject-reported symptoms and activity level. The answers should reflect symptoms and activity level during the previous 24 hours. The PUCAI scores of the last 2 days prior to each study visit will be averaged and used for the PUCAI scores for each study visit. The total PUCAI score will be rounded up to the next 5-point interval as applicable. In order to account for unavailable or excluded diary entries as per the provisions given below diary entries for the PUCAI score of the most recent 2 days within 10 days prior to each study visit will be used.

Diary entries of the following days should not be included in the 2 days prior to the visit that are evaluated for the PUCAI score: (1) the day the subject received medication for

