bowel preparation prior to endoscopy, (2) the day the subject underwent an endoscopy, and (3) 2 days following the endoscopy. Earlier diary entries will be used accordingly in order to provide the most recent data for 2 days prior to the respective study visit.

The subscore for the number of stools per 24 hours during days which a subject received anti-diarrheal medication will be scored as 15.

Mayo Score

The following definitions will be used:

Table 3. Definitions

Term	Definition
Mayo Score	Composite score of UC disease activity based on the subscores of stool frequency (0 – 3), rectal bleeding (0 – 3), physician's global assessment (0 – 3) and endoscopic subscore (0 – 3). This score ranges from 0 – 12 points with higher scores representing more severe disease.
Partial Mayo Score	Composite score of UC disease activity based on the subscores of stool frequency, rectal bleeding, and physician's global assessment and DOES NOT include the endoscopic subscore. This score ranges from 0 – 9 points.
9 point Mayo Score (without SFS)	Composite score of UC disease activity based on the subscores of rectal bleeding (0 – 3), physician's global assessment (0 – 3) and endoscopic subscore (0 – 3). This score ranges from 0 – 9 points with higher scores representing more severe disease.
9 point Mayo Score (without PGA)	Composite score of UC disease activity based on the subscores of stool frequency (0 – 3), rectal bleeding (0 – 3), and endoscopic subscore (0 – 3). This score ranges from 0 – 9 points with higher scores representing more severe disease.
9 point Mayo Score (without RBS)	Composite score of UC disease activity based on the subscores of stool frequency (0 – 3), physician's global assessment (0 – 3) and endoscopic subscore (0 – 3). This score ranges from 0 – 9 points with higher scores representing more severe disease.
6 point Mayo Score (without SFS and endoscopy subscore)	Composite score of UC disease activity based on the subscores of rectal bleeding (0 – 3) and physician's global assessment (0 – 3). This score ranges from 0 – 6 points with higher scores representing more severe disease.
6 point Mayo Score (without PGA and endoscopy subscore)	Composite score of UC disease activity based on the subscores of stool frequency (0 – 3) and rectal bleeding (0 – 3). This score ranges from 0 – 6 points with higher scores representing more severe disease.

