5.3.3.2 Secondary Variables

Ranked secondary efficacy variables are:

1. Proportion of subjects in Mayo clinical response at Week 52 in Week 8 responders per PMS;
2. Proportion of subjects who achieve mucosal healing at Week 52 as measured by Mayo endoscopy subscore (defined as ≤ 1) in Week 8 responders per PMS;
3. Proportion of subjects who achieve Mayo clinical remission at Week 52 in Week 8 remitters per PMS;
4. Proportion of subjects receiving corticosteroid at Baseline who have discontinued corticosteroid prior to Week 52 and are in Mayo clinical remission at Week 52 in Week 8 responders per PMS.

Additional exploratory secondary analyses will be performed for:

- Proportion of subjects in PMS clinical remission at Week 52 in Week 8 responders per PMS;
- Proportion of subjects in PUCAI remission (defined as < 10) at Week 8;
- Proportion of subjects in PUCAI response (defined as a decrease in PUCAI ≥ 20 points from Baseline) at Week 8;

- Proportion of subjects in PUCAI remission (defined as < 10) at Week 52 in Week 8 responders per PMS;
- Proportion of subjects in PUCAI response (defined as a decrease in PUCAI ≥ 20 points from Baseline) at Week 52 in Week 8 responders per PMS;
- Proportion of subjects receiving corticosteroid at Baseline who discontinue corticosteroid prior to Week 52 and are in PUCAI remission at Week 52 in Week 8 responders per PMS;
- Change from Baseline in total IMPACT III Quality of Life scores over time for subjects at least 9 years old at Baseline;
- Change from Baseline in WPAI scores over time;
- Change from Baseline in "z" scores for height (observed height velocity [cm/yr] – mean height velocity for age and sex [cm/yr]/SD of the mean) at Week 26 and Week 52;
- Change from Baseline in BMI at Week 26 and Week 52;
- Change from Baseline in "z" scores for weight-for-age at Week 26 and Week 52;
- Proportion of subjects at appropriate Tanner stage at Week 26 and Week 52 compared to Baseline;
- Proportion of subjects in PMS response over time;
- Proportion of subjects in PMS remission over time;
- Proportion of subjects in PUCAI response over time;
- Proportion of subjects in PUCAI remission over time;
- Change from Baseline in number of daily stool over time;
- Change from Baseline in albumin and total protein at different time points;
- Change from Baseline in hemoglobin, hematocrit, red blood cell count at different time points;
- Change from Baseline in hs-CRP levels at different time points;

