Multiple Imputation (MI): The MI analysis will impute missing data multiple times under appropriate random variation and thus generate multiple imputed "pseudocomplete" datasets. Results will be aggregated across the multiple imputed datasets, overcoming drawbacks of the single imputation methods. PROC MI will be used to generate multiple datasets. Specifically, visits will be imputed in order, where later visits are imputed based upon all previous visits, baseline, treatment group, demographics and other key baseline characteristics. Analysis will first be performed on each of the multiple imputed datasets, and PROC MIANALYZE will then be used to aggregate the results for the final statistical inference. In Multiple Imputation, subjects who discontinued due to lack of efficacy or received rescue medication will be forced in as non-responders. The MI analysis will only be performed as sensitivity analysis.

Missing Items on Questionnaire Scales:

Mayo scores (and alternative composite scores) can only be calculated if all subscores included are collected. If one or more subscores are missing, the Mayo score will be considered missing. No imputations will be made. The symptoms of stool frequency and rectal bleeding are scored as a 5 day average of daily values from up to 14 days preceding the visit, rounded to one decimal place. The most recent consecutive days will be used. If consecutive days are not available, then non-consecutive days can be used. Diary entries for stool frequency and rectal bleeding should not be included in the 5 days prior to the

[figure not shown]
visit that are evaluated for these subscores for the following days: (1) the day the subject received medication for bowel preparation prior to endoscopy, (2) the day the subject underwent an endoscopy, and (3) 2 days following the endoscopy. Earlier diary entries will be used accordingly in order to provide the most recent data for 5 days prior to the respective study visit. If less than 3 days of diary data are available, stool frequency and rectal bleeding subscores will be considered missing.

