When calculating **PUCAI**, if more than 3 subscores are missing then PUCAI will be considered missing. Otherwise, for missing subscores, the last available post-baseline value for the respective subscore will be carried forward to compute the total PUCAI score. The subscores of abdominal pain, rectal bleeding, stool consistency, number of stools per 24 hours, nocturnal stools and activity level are scored as a 2 day average, rounded to one decimal place. The most recent consecutive days will be used. If consecutive days are not available, then non-consecutive days can be used.

When calculating **IMPACT III** total score, if 4 or more of the items are missing then IMPACT III total score and all subscores will be considered missing. Otherwise, if there are 3 or fewer missing answers, the average of non-missing values will be used to replace the missing items for the total score and subscore calculation. If for subscores consisting of only 3 items (see 'Score Definitions' later in this Section), all of these items are missing and are replaced per above convention, a footnote will be added indicating for how many subjects the subscore included in the analysis has been fully imputed.

When calculating the **WPAI** scores, the following computational notes should be followed.

[figure not shown]
- Define Employment as a binary YES or NO variable where YES corresponds to "Employed" and NO corresponds to "Not Employed":
 - A subject will be considered EMPLOYED at a given visit if Q1 = YES or Q2 > 0 or Q4 > 0.

- A subject will be considered UNEMPLOYED at a given visit if Q1 = NO and no positive hours recorded under Q2 and Q4 (i.e., if Q1 = NO AND $Q2 \le 0$ AND $Q4 \le 0$, then UNEMPLOYED).
- Employment status for a subject will be considered missing at a given visit if Q1 = missing and no positive hours recorded under Q2 and Q4.
- If a subject is UNEMPLOYED or employment status is missing, then S1, S2, and S3 will be set to missing.
- If Q2 = 0 and Q4 = 0 or missing then Q2/(Q2 + Q4) = missing (i.e., S1 = missing).
- If Q2 = 0 and Q4 = 0, then set S3 to missing.
- If Q2 is missing or Q4 is missing, then set S1 and S3 to missing.
- If Q4 = missing, then DO NOT set Q5 = missing.
- If Q5 is missing, then apply the following rules:
 - \circ If Q2 > 0, Q4 = 0, and Q5 = missing, then S3 = 100%.
 - \circ If Q2 = 0, Q4 > 0, and Q5 = missing, then S3 is missing.
 - If Q2 > 0, Q4 > 0, and Q5 = missing, then S3 is missing.

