- Change from Baseline in number of daily stool (last non-missing value prior to the respective visit) over time;
- Change from Baseline in albumin and total protein over time;
- Change from Baseline in hemoglobin, hematocrit, red blood cell count over time;
- Change from Baseline in hs-CRP levels over time;
- Proportion of subjects with EIM at Baseline, Week 26 and Week 52 (OC analysis);
- Proportion of subjects with Mayo endoscopy subscore of 0 or 1 (without friability) at Week 52;

[figure not shown]
- Proportion of subjects being hospitalized (all cause) during the study (OC analysis);
- Proportion of subjects being hospitalized (UC-related) during the study (OC analysis);
- Proportion of subjects undergoing colectomy during the study (OC analysis);
- Proportion of subjects receiving systemic corticosteroids at Baseline who have discontinued systemic corticosteroids prior to Week 52* and completed the study (Week 52) (OC analysis);
- Correlation between PMS and PUCAI at different time points;
- Proportion of subjects in a 9 point Mayo (without SFS) clinical remission (defined as ≤ 2 and no individual subscore > 1) at Week 52 in Week 8 responders per PMS;
- Proportion of subjects in a 9 point Mayo (without PGA) clinical remission (defined as ≤ 2 and no individual subscore > 1) at Week 52 in Week 8 responders per PMS;
- Proportion of subjects in a 9 point Mayo (without RBS) clinical remission (defined as ≤ 2 and no individual subscore > 1) at Week 52 in Week 8 responders per PMS;
- Proportion of subjects in a 6 point Mayo (without SFS and endoscopy subscore) clinical remission (defined as ≤ 1) at Week 8;
- Proportion of subjects in a 6 point Mayo (without PGA and endoscopy subscore) clinical remission (defined as ≤ 1) at Week 8;
- Proportion of subjects in a 6 point Mayo (without RBS and endoscopy subscore) clinical remission (defined as ≤ 1) at Week 8;
- Change from Baseline in Mayo score at Week 52;
- Change from Baseline in PMS over time;
- Change from Baseline in PUCAI over time;
- Change from Baseline in endoscopy subscore at Week 52;
- Change from Baseline in SFS over time;
- Change from Baseline in RBS over time;
- Change from Baseline in PGA over time.

*discontinued systemic corticosteroids prior to Week 52: stop date of corticosteroid must be before the min (nominal day of Week 52 per Visit Window table, visit date at which the endpoint was measured).

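### The SAP's day-selection rules let bowel-preparation days into PUCAI and the daily stool count at endoscopy visits; for PUCAI the protocol excludes those days and the SAP does not

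*SAP*

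**What the plan says.** **Daily stool count.** The protocol (5.3.3.2) only names the endpoint: "Change from Baseline in number of daily stool over time". SAP 10.4 adds the day rule: "Change from Baseline in number of daily stool (last non-missing value prior to the respective visit) over time". Neither document excludes any day.

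**PUCAI in the protocol.** Section 5.3.1.1 averages the 2 days before the visit and then limits which days qualify: "Diary entries of the following days should not be included in the 2 days prior to the visit". The listed days are the day of medication for "bowel preparation prior to endoscopy, (2) the day the subject underwent an endoscopy, and (3) 2 days following the endoscopy". Replacement entries come from the most recent 2 days within 10 days of the visit. The total is then rounded up to the next 5 points.

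**PUCAI in the SAP.** Section 6.0 says that "number of stools per 24 hours, nocturnal stools and activity level are scored as a 2 day average, rounded to one decimal place", and then: "The most recent consecutive days will be used". Non-consecutive days are allowed if consecutive ones are missing. The paragraph contains no exclusion, no 10-day limit and no rounding up of the total.

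**Mayo subscores in the SAP.** The paragraph just before the PUCAI one does write out the exclusion, in a sentence that begins "Diary entries for stool frequency and rectal bleeding should not be included in the 5 days prior to the" and names the same three kinds of day. Its wording covers stool frequency and rectal bleeding only.

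**When endoscopy happens.** Protocol 5.3.1.1 and Table 1 place an endoscopy at Screening, at Week 52, and at premature discontinuation if that occurs after Week 26.

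**The concern.** SAP 3.0 says that its conventions guide the programming. A programmer who reads the two adjacent paragraphs of SAP 6.0 would reasonably take the exclusion as specific to the Mayo subscores and score PUCAI from the latest days, whatever they are. At a visit with endoscopy, those are the days that the protocol meant to remove.

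Three of the eleven endpoints that SAP 10.4 compares between doses are Week 52 PUCAI endpoints: remission, response, and steroid-free remission. PUCAI over time, its change from Baseline and its correlation with PMS would also be touched. In that correlation, the diary part of PMS would be free of preparation days and PUCAI would not. The stool count rests on one day, so nothing dilutes the effect there.

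**Working it through.** **Scale.** The PUCAI item maxima in Appendix C and SAP 6.0 are pain 10, bleeding 30, consistency 10, stool number 15, nocturnal stools 10 and activity 10. Their sum is 10 + 30 + 10 + 15 + 10 + 10 = 85, which matches the stated maximum. No power or alpha statement in the plan uses PUCAI or the stool count.

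**Which days can enter.** Let V be the visit day. Assume that preparation is taken the day before endoscopy and that the diary days used are V−1 and V−2.
- Endoscopy on V: V−1 is the preparation day. It is one of the 2 PUCAI days and is the whole stool count.
- Endoscopy on V−1: V−2 is the preparation day and V−1 the endoscopy day. The protocol would drop both.
- Endoscopy on V−2, V−3 or V−4: at least one PUCAI day is the endoscopy day or one of the 2 days after it.
- Endoscopy on V−5 or earlier: both days are eligible.

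**PUCAI, one preparation day out of 2.** Take a child who scores 0 on clean days. The average is (0 + x)/2, where x is the preparation-day score. Item points are from SAP 6.0; the symptoms are assumed. Remission is a score below 10.

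| Preparation-day symptoms | x | Average | Remission on SAP average? | If total rounded up to next 5 |
|---|---|---|---|---|
| 3–5 stools only | 5 | 2.5 | yes | 5, yes |
| 6–8 stools only | 10 | 5.0 | yes | 5, yes |
| >8 stools only | 15 | 7.5 | yes | 10, no |
| 3–5 stools, unformed | 5 + 10 = 15 | 7.5 | yes | 10, no |
| 6–8 stools, unformed | 10 + 10 = 20 | 10.0 | no | 10, no |
| >8 stools, unformed | 15 + 10 = 25 | 12.5 | no | 15, no |
| >8 stools, unformed, nocturnal | 15 + 10 + 10 = 35 | 17.5 | no | 20, no |

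If both days carried the last three patterns, the averages would be 20, 25 and 35. With the protocol's exclusion, every row returns to 0.

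**PUCAI response.** Response needs a fall of at least 20 points. For the same child, a Week 52 score of 17.5 loses a true response only if Baseline PUCAI is below 17.5 + 20 = 37.5. A score of 10.0 loses it only if Baseline is below 30.

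**Rounding.** The average of two multiples of 5 is a multiple of 2.5, so rounding subscores to one decimal changes nothing. Rounding the total up to the next 5 turns 2.5 into 5 and 7.5 into 10. For remission, the two rules therefore disagree at exactly one value, 7.5.

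**Stool count.** Assume 7 stools a day at Baseline and 1 a day when well. The true change is 1 − 7 = −6. If the last value is a preparation day with 9, 12 or 15 stools, the recorded change is +2, +5 or +8.

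**The case against.** For PUCAI, the protocol already has the right exclusion, and the SAP describes itself as elaborating the protocol. Silence is not repeal. The SAP also leaves out the protocol's scoring of days with anti-diarrheal medication, so an omission there is weak evidence of intent. This stands to a degree: nothing shows that the sponsor chose to count preparation days. But the SAP gives a positive instruction on which days to use, and that instruction conflicts with the protocol at endoscopy visits. Consulting the protocol would not help the stool count, where neither document has a rule.

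The sizes above are hypothetical. The documents give neither the interval between endoscopy and visit nor the preparation used. Flexible sigmoidoscopy is allowed, and milder effects leave the child in remission on the SAP average. This stands in full. A reader might infer that any preparation day turns remission into failure; the table shows that it does not.

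A reader might also infer that only Baseline and Week 52 are exposed. Discontinuation endoscopies after Week 26 can fall in other analysis windows, such as Week 34 or Week 42. Under NRI, a child who stops before the Week 52 window is a Week 52 failure anyway, so that route matters for over-time summaries and, where LOCF is applied, for continuous changes. Contamination at Baseline is improbable. The screening endoscopy must be read centrally to establish eligibility and may be up to 56 days old, while the Baseline stool count in SAP 7.1 is confined to Rx Days −1 to 1.

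**Conclusion.** The gap is real and worth closing, but its reach is limited. For PUCAI it is a discrepancy between SAP and protocol; for the stool count it is a missing rule. Followed as written, the SAP can score a child with true PUCAI 0 at 10.0 to 17.5, not in remission, when one of the 2 days is a preparation day with at least 6 unformed stools. Milder effects give 7.5 or less, which is still remission under the SAP's rounding. The result rests on assumed symptoms and on the endoscopy falling close to the visit. The number of children affected cannot be estimated from the documents.

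Three stronger readings are not supported. A reader might think that the main conclusions are at risk. They are not: the affected endpoints are all exploratory, the Mayo diary subscores are protected in both documents, and power and alpha do not change. A reader might carry the remission consequence over to the stool count, but that endpoint has no remission threshold; only its change from Baseline is biased upward. A reader might expect a bias between doses. All maintenance groups have the same Week 52 endoscopy, so the effect there is mainly non-differential misclassification. Within each group, it lowers estimated PUCAI remission and response.

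**What to change.** 1. In the PUCAI paragraph of SAP 6.0, carry over the protocol's rule: drop the preparation day, the endoscopy day and the 2 following days, and use the most recent 2 eligible days within 10 days of the visit.
2. In SAP 10.4, take the daily stool count as the last non-missing value from an eligible day under the same exclusion. Keep the single-day definition. Substituting a mean over several days would redefine the endpoint and is not needed to remove the problem.
3. In the same edit, make the protocol and SAP agree on PUCAI rounding and state the rule once, since a total of 7.5 is remission under one and not under the other.

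The cost is a few lines of SAP text and some programming; the exclusion dates are already needed for the Mayo subscores. The only analytic price is that some stool counts will come from a slightly earlier day.
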